## PROTOCOL SUMMARY

Protocol Title:
Phase I/II trial of MLN9708 plus Pomalidomide and Dexamethasone for Relapsed or Relapsed Refractory Multiple Myeloma
Brief Protocol Title for the Lay Public (if applicable):
Phase I/II trial of MLN9708 plus Pomalidomide and Dexamethasone for Relapsed or Relapsed Refractory Multiple Myeloma
Study Phase:
Phase I/II
Participating Sites:

 
▪ City of Hope
 
▪ Mayo Clinic: Rochester and Arizona
 
▪ Winship Cancer Institute of Emory University School of Medicine
 
▪ Sarah Cannon Research Institute Center
 

Rationale for this Study:

Novel drugs are needed for the treatment of relapsed or relapsed refractory multiple myeloma. The combination of proteasome inhibitor (PI) and immunomodulating (IMiD) agents has produced significant responses. Many patients are exposed to these classes of drugs earlier in the course of therapy, for patients who relapse after agents such as the PI bortezomib and the IMiD lenalidomide, newer agents are now available or in development including pomalidomide and MLN9708. Pomalidomide is an IMiD that is active even in patients who are refractory to other IMiDS such as lenalidomide. MLN9708 is a PI that has shown activity in patients refractory to bortezomib. MLN9708 has shown activity in Phase I/II trials and pomalidomide and dexamethasone have shown activity in Phase I/II and III trials. Hence combining the two agents and including dexamethasone for synergy could potentially induce responses in this refractory patient population.

Objectives:

Phase I:
 
Primary:
 
 
1) To determine the recommended phase II dose (RP2D) of MLN9708 when given in combination with pomalidomide and dexamethasone, in patients with relapsed or relapsed/refractory multiple myeloma.
 
 
Secondary:
 
 
2) To evaluate the safety of MLN9708 at each dose level when given as part of a three drug combination by assessing the following: 
 
- type, frequency, severity, attribution, time course and duration of adverse events
 
- clinical laboratory tests at various points in the study
 
 
 

**Phase II:****Primary:**

1. To estimate the response rate and to evaluate the antitumor activity of the three drug combination: MLN9708 (at the RP2D), pomalidomide and dexamethasone, in patients with relapsed or relapsed/refractory multiple myeloma.

**Secondary:**

At the RP2D, for the three drug combination:

2. To characterize and evaluate toxicities, including type, frequency, severity, attribution, time course and duration.
3. To obtain estimates of response duration, depth of response, clinical benefit response, and survival (overall and progression-free).

**Study Design:**

This study will be conducted as a multicenter phase I/II trial.

The phase I portion will follow a standard 3+3 dose escalation design, to evaluate toxicities associated with MLN9708 when given in combination with pomalidomide and dexamethasone. Two doses of MLN9708, 3mg and 4 mg, will be tested in up to three possible dose levels:

Schedule: Each cycle is 28 days			
Dose Level	Pomalidomide	MLN9708	Dexamethasone*
-1	3mg daily on days 1-21	3 mg on days 1, 8 and 15	40 mg on days 1, 8, 15 and 22
1	4 mg daily on days 1 - 21	3 mg on days 1, 8 and 15	40 mg on days 1, 8, 15 and 22
2	4 mg daily on days 1 - 21	4 mg on days 1, 8 and 15	40 mg on days 1, 8, 15 and 22

\*: Patients >75 years, at the time of trial registration, will receive a dexamethasone starting dose of 20mg on the same set schedule.

The RP2D identified in the phase I portion of the study will be brought forward for activity evaluation.

The phase II portion of this study will implement a Gehan two-stage design to estimate the response rate and to evaluate the activity of MLN9708 when given in combination with pomalidomide and dexamethasone (Gehan, 1961).

**Endpoints:****Phase I:**

The primary endpoint is toxicity. Toxicity will be graded according to the NCI-Common

Terminology Criteria for Adverse Events version 4.03. Dose limiting toxicity (DLT) is defined in section 7.3 of the protocol.

**Phase II:**

The primary endpoint is response rate (sCR/CR/VGPR and PR) and is based on the International Myeloma Working Group (IMWG) criteria.

**Sample Size:**

**Phase I:**

The phase I study will follow a 3+3 design, to evaluate toxicities associated with MLN9708 when given in combination with pomalidomide and dexamethasone. Two doses of MLN9708 (3 mg and 4 mg) will be tested in up to three possible dose levels. In the phase I portion of this study, the total sample size will depend on the number of dose levels evaluated to determine the RP2D. While the phase I study is expected to enroll and treat 9 patients (3 patients at dose level 1, and another 6 at dose level 2-assuming the 4mg dose is well tolerated), a maximum of 18 patients could be treated (6 patients treated at each dose level).

**Phase II:**

The phase II portion of the study is expected to enroll a minimum of 9 and a maximum of 25 patients. The six patients treated at the RP2D in the phase I portion of the study will count toward the 25 patients required; given this, we expect to enroll only 19 new patients during the phase II trial portion. The sample size is based on the desire to achieve a (promising) target response rate of >30%.

**Estimated Duration of the Study**

Accrual, for both phases, is expected to be completed in 26 months; with approximately 2 patients enrolled each month. Patients will be treated in 28-day treatment cycles until disease relapse, progression or unacceptable toxicity, withdrawal of consent, or protocol specified parameters to stop treatment. Patients who discontinue study treatment for reasons other than disease relapse/progression will continue to have disease assessments per International Myeloma Working Group (IMWG) criteria until relapse or progression, initiation of new anticancer treatment, or death whichever occurs first. Patients will be followed to collect further anticancer treatment and survival information until death, loss to follow-up, withdrawal of consent, study termination or up to 24 months post treatment.

**Summary of Patient Eligibility Criteria:**

**Inclusion Criteria**

Each patient must meet all of the following inclusion criteria to be enrolled in the study:

1. Male or female patients 18 years or older.
2. Voluntary written informed consent must be given before performance of any study related procedure not part of standard medical care, with the understanding that consent may be withdrawn by the patient at any time without prejudice to future medical care.
3. Females of childbearing potential (FCBP) must have a negative serum or urine pregnancy test with a sensitivity of at least 25 mIU/mL within 10 – 14 days prior to and again within 24 hours of starting pomalidomide and must either commit to continued abstinence from heterosexual intercourse or begin two acceptable methods

of birth control, one highly effective method and one additional effective method at the same time, at least 28 days before she starts taking pomalidomide through 90 days after the last dose of study drug. FCBP must also agree to ongoing pregnancy testing. Men must agree to use a latex condom during sexual contact with a FCBP even if they have had a vasectomy from the time of signing the informed consent form through 90 days after the last dose of study drug.

4. All patients must be registered in and must comply with all requirements of the POMALYST REMSTM program.
5. Patients must have a diagnosis of relapsed or relapsed and refractory Multiple Myeloma with a minimum of one prior regimen and a maximum of 5 prior regimens.
6. Patients must have had therapy with a proteasome inhibitor and lenalidomide and be refractory to lenalidomide according to the IMWG definition of refractory disease (progressive disease on or within 60 days of stopping lenalidomide).
7. Patients must have measurable disease defined as one of the following:
  - Serum M protein  $\geq 0.5$  g/dL
  - Urine M protein  $\geq 200$  mg/24 hours
  - Serum free light chain  $\geq 10$  mg/dL provided the FLC ratio is abnormal.
8. Eastern Cooperative Oncology Group (ECOG) performance status and/or other performance status 0, 1, or 2.
9. Patients must meet the following clinical laboratory criteria:
  - Absolute neutrophil count (ANC)  $\geq 1,000/\text{mm}^3$
  - Platelet count  $\geq 75,000/\mu\text{L}$  for patients in whom  $< 50\%$  of bone marrow nucleated cells are plasma cells; or a platelet count  $\geq 50,000/\mu\text{L}$  for patients in whom  $\geq 50\%$  of bone marrow nucleated cells are plasma cells. Platelet transfusions are not allowed within 3 days of last platelet assessment to confirm eligibility.
  - Total bilirubin  $\leq 1.5 \times$  the institutional upper limit of normal range (IULN).
  - Alanine aminotransferase (ALT) and aspartate aminotransferase (AST)  $\leq 3 \times$  IULN (institutional upper limit of normal range)
  - Calculated creatinine clearance  $\geq 45 \text{ mL/min}$  (Appendix 15.2)

### Exclusion Criteria

Patients meeting any of the following exclusion criteria are not to be enrolled in the study:

1. Female patients who are pregnant or breastfeeding or have a positive serum pregnancy test during the screening period.
2. Failure to have fully recovered (i.e.,  $\leq$  Grade 1 toxicity) from the reversible effects of prior chemotherapy.
3. Prior treatment with a multidrug regimen containing pomalidomide except the 2 drug combination of pomalidomide and dexamethasone.
4. Major surgery within 14 days before enrollment.
5. Radiotherapy within 14 days before enrollment. If the involved field is small, 7 days will be considered a sufficient interval between treatment and administration of the MLN9708.
6. Central nervous system involvement.
7. Infection requiring systemic antibiotic therapy or other serious infection within 14 days before study enrollment.

8. Evidence of current uncontrolled cardiovascular conditions, including uncontrolled hypertension, uncontrolled cardiac arrhythmias, symptomatic congestive heart failure, unstable angina, or myocardial infarction within the past 6 months.
9. Systemic treatment, within 14 days before the first dose of MLN9708, with strong inhibitors of CYP1A2 (fluvoxamine, enoxacin, ciprofloxacin), strong inhibitors of CYP3A (clarithromycin, telithromycin, itraconazole, voriconazole, ketoconazole, nefazodone, posaconazole) or strong CYP3A inducers (rifampin, rifapentine, rifabutin, carbamazepine, phenytoin, phenobarbital), or use of Ginkgo biloba or St. John's Wort.
10. Unable or unwilling to undergo antithrombotic prophylaxis.
11. Ongoing or active systemic infection, active hepatitis B or C virus infection, or known human immunodeficiency virus (HIV) positive.
12. Any serious medical or psychiatric illness that could, in the investigator's opinion, potentially interfere with the completion of treatment according to this protocol.
13. Known allergy to any of the study medications, their analogues, or excipients in the various formulations of any agent.
14. Known GI disease or GI procedure that could interfere with the oral absorption or tolerance of MLN9708 or pomalidomide including difficulty swallowing.
15. Diagnosed or treated for another malignancy within 2 years before study enrollment or previously diagnosed with another malignancy with evidence of residual disease. Patients with nonmelanoma skin cancer or carcinoma in situ of any type are not excluded if they have undergone complete resection.
16. Patient has > Grade 2 peripheral neuropathy on clinical examination during the screening period.
17. Participation in other clinical trials, including those with other investigational agents not included in this trial, within 21 days of the start of this trial and throughout the duration of this trial (for all other standard therapies, no treatment within 14 days of the start of this trial).
18. Patients who are pomalidomide refractory, defined as patients who progress on or within 60 days of pomalidomide when given as a single agent or with dexamethasone.

#### **Investigational Product Dosage and Administration:**

MLN9708: 3mg or 4 mg oral; Pomalidomide: 3mg or 4mg oral; Dexamethasone: 40 mg oral (Note: Patients >75 years, at the time of trial registration, will receive a Dexamethasone dose of 20 mg on the same set schedule.)

#### **Clinical Observations and Tests to be Performed:**

Standard myeloma restaging studies (SPEP, UPEP, Bone Marrow Biopsy, Serum and Urine Immunofixation, Serum free lites, when applicable). Refer to the Table of Assessments for complete details.

#### **Statistical Considerations:**

##### **Phase I:**

The primary objective of the phase I study is to determine the recommended phase II dose (RP2D) of MLN9708 when given in combination with pomalidomide and dexamethasone, in patients with relapsed or relapsed/refractory multiple myeloma.

The phase I study will follow a 3+3 design for enrollment with dose escalation, or expansion of a cohort on the basis of the occurrence of dose limiting toxicities (DLTs) during cycle 1. Two doses of MLN9708 will be tested in up to three possible dose levels (dose level -1 and dose level 1: 3mg / dose level 2: 4 mg, administered on days 1, 8 and 15 of a 28 day cycle). The highest dose level that produces  $\leq 1/6$  DLTs in cycle 1 will be the maximum tolerated dose (MTD). The RP2D of MLN9708 and pomalidomide will generally be the MTD, but it may be less than the MTD based on a review of available data/cumulative toxicities from phase I.

**Analysis:** Observed toxicities will be summarized in terms of type (organ affected or laboratory determination), severity, time of onset, duration, probable association with the study regimen and reversibility or outcome. Baseline information (e.g. the extent of prior therapy) and demographic information will be presented as well to describe the patients treated in this study.

**Phase II:**

The primary objective is to estimate the response rate and to evaluate the antitumor activity of the three drug combination: MLN9708 (at the RP2D), pomalidomide, and dexamethasone, in patients with relapsed or relapsed/refractory multiple myeloma. The primary endpoint is a confirmed tumor response of sCR/CR/VGPR or PR and is based on IMWG Criteria. A single cycle of treatment will be given in a 28 day cycle. Each patient's disease status will be evaluated at baseline. Response will be assessed at the end of each cycle/just prior to the start of each cycle and is based on the IMWG criteria.

**Statistics/Sample Size and Accrual:** The phase II portion of this study will implement a Gehan two-stage design to estimate the response rate and to evaluate the activity of MLN9708 when given in combination with pomalidomide and dexamethasone (Gehan 1961). The phase II portion of the study is expected to enroll a minimum of 9 and a maximum of 25 patients. The six patients treated at the RP2D in the phase I portion of the study will count toward the 25 patients required; given this, we expect to enroll only 19 new patients on the phase II trial. The sample size is based on the desire to estimate the response rate with at most 10% standard error, and early stopping if the combination is unexpectedly ineffective.

At stage 1, 9 patients will be entered on the study. If 0 responses are seen in the first 9 patients treated, the study will be terminated and the true regimen response will be declared  $\leq 30\%$ . If at least 1 patient responds, the trial will continue to the second stage. Because patients treated during the phase I portion of the trial at the dose selected for the phase II trial will be counted ( $n=6$ ), only 3 additional patients will be enrolled at stage 1. Under this design if the study regimen is  $>30\%$  effective, there would be  $\sim 95.6\%$  chance of at least one success.

At stage 2, 16 additional patients will be entered. This accrual provides for estimation of the response rate with no more than 10% standard error.

**Analysis:** The overall response rate will be calculated as the percent of evaluable patients that have confirmed sCR/CR/VGPR or PR; the clinical benefit response rate will be calculated as the percent of evaluable patients that have confirmed sCR/CR/VGPR/PR/ MR or SD; exact

95% confidence intervals will be calculated for these estimates. Response rates will also be evaluated based on number and type of prior therapy(ies). Time to response, duration of response, and survival will be estimated using the product-limit method of Kaplan and Meier.

**Sponsor**

Investigator Initiated Trial - City of Hope

**Case Report Forms**

This trial will utilize the Medidata RAVE® Electronic Data Capture system.

## SCHEDULE OF EVENTS

PROCEDURES	Screen	Cycle 1 Each cycle is 28 days				Cycle 2+* Each cycle is 28 days				End of Treatment	Post Study Follow Up
		-21d to -1d	Day 1	Day 8	Day 15	Day 22	Day 1	Day 8	Day 15*	Day 22	
Window		± 1	± 1	± 1	± 1	± 1	± 1	± 1	± 1		
Informed Consent	X										
Medical History, Demographics	X										
Concomitant Medications	X	X	X	X	X	X	X		X	X	X 
PE, Height  , Weight, ECOG	X					X				X	
Toxicity Evaluation		X				X				X	
Vital Signs (HR, Temp, BP)	X	X				X				X	
12-lead ECG 	X 									X	
Education and counseling guidance document 	X					X				X	
CBC 	X	X	X	X	X	X				X	
Serum Chemistry 	X			X		X				X	
Neurological exam 	X					X				X	
PT/PTT 	X									X	
Pregnancy test [FCBP] 	X	X	X	X	X	X		X 		X 	
Extramedullary disease 	X					X				X	
Skeletal Survey 	X										
Bone Marrow Aspiration/Biopsy 	X					X					
Myeloma-specific lab tests 	X					X				X	
MILN9708 Administration		X	X	X		X	X	X			
Dexamethasone		X	X	X	X	X 	X 	X 	X 		
Pomalidomide Administration		Days 1 - 21				Days 1 – 21					

PROCEDURES	Screen	Cycle 1 Each cycle is 28 days				Cycle 2+* Each cycle is 28 days				End of Treatment	Post Study Follow Up
	-21d to -1d	Day 1	Day 8	Day 15	Day 22	Day 1	Day 8	Day 15*	Day 22		
Follow for PD and survival											X 

- 1) Measured at screening only.
- 2) FCBP - A female of childbearing potential is a sexually mature woman who: 1) has not undergone a hysterectomy or bilateral oophorectomy; or 2) has not been naturally postmenopausal for at least 24 consecutive months. Pregnancy tests for FCBP must be performed within 10 to 14 days and again within 24 hours of initiation of therapy. Repeat pregnancy test every week for the first 4 weeks and then every 28 days while on therapy and during interruptions in therapy and 28 days following discontinuation of pomalidomide. Women with irregular menstruation must have pregnancy testing every 14 days while on therapy and during interruptions and 14 and 28 days after discontinuation of Pomalidomide. For Cycle 2 and forward, the D15 pregnancy test (if required) can be done locally and results faxed to the main institution.
- 3) ECG (12-Lead) should be performed and read locally.
- 4) All patients must be counseled about pregnancy precautions, risks of fetal exposure and other risks. All patients enrolled into this trial, must be registered in and must comply with all requirements of the POMALYST REMS™ program.
- 5) CBC to be performed and reviewed by clinician within 24 hours of day of dosing (first day of each cycle). Alternately, a STAT CBC may be drawn on day of dosing, however should be reviewed prior to administration of investigational product(s). Serum Chemistry to be performed and reviewed by the investigator within 24 hours of day of dosing (first day of each cycle). Alternately, a STAT CMP may be drawn on day of dosing however should be reviewed by the investigator prior to administration of investigational product(s). Chemistry includes: glucose, calcium, albumin, total protein, sodium, potassium, BUN, creatinine, ALP, ALT, AST, bilirubin and uric acid (uric acid to be drawn at screening and then as needed based on tumor lysis syndrome risk). Weight and serum creatinine will be used to calculate creatinine clearance by Cockcroft-Gault equation (see appendix 15.2).
- 6) Neurological assessment required at screening and Day 1 of Cycle 2+.
- 7) Extramedullary Disease: prior to study (28 days), testing required only if extramedullary disease is present, every 12 weeks (if present at screening) or upon clinical suspicion of progressive disease (if present at screening). This may include CT scan of the abdomen/pelvis, CT or x-ray of the chest, ultrasound of the liver/spleen or abdomen.
- 8) Skeletal survey (including skull, all long bones, pelvis and chest) with tumor measurements (measurements required if plasmacytomas are present). Also required if previous survey >28 days from study entry and at any time when clinically indicated.
- 9) A bone marrow aspiration and biopsy is required at screening; Repeat bone marrow biopsy/aspirate as appropriate to confirm achievement of response (aspirate only—biopsy not required).
- 10) Myeloma lab tests: B2Microglobulin (collected at screening only); serum immunoelectrophoresis, immunoglobulin assay, M band quantitation by immunofixation, free light chain and 24 hour urine collection for Bence Jones protein to be performed at baseline prior to study, prior to each cycle (to confirm complete response and in patients with urine only measurable disease) thereafter and at time of end of treatment (if last tests were > 3 weeks).
- 11) End of study follow-up to be completed every three months for two years to include second primary malignancies, new therapies for the treatment of MM only (not all concomitant medication) and survival.
- 12) Due to the risk of blood clots while on Pomalidomide, if patient is started on warfarin, routine monitoring of INR should occur (as per your institutional guidelines).
- 13) After the patient has been on Dexamethasone over one year, the patient can discontinue Dexamethasone at their next scheduled visit.

\*Additional tests to be performed at the beginning of each cycle and at any reasonable time point during treatment if indicated for monitoring of drug profile/safety or, for disease/health status at the discretion of the clinical investigator. Starting with Cycle 2 and forward, the patient is not required to come to the main hospital/institution for a Day 15 visit. The patient can be seen locally by their physician at their discretion.

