**Table 1-1 Ongoing Studies of Oral MLN9708**

Trial/ Population	Description	Doses Investigated
C16003 RRMM N = 58	PO, twice weekly (TW), single agent	0.24-2.23 mg/m  , TW MTD: 2.0 mg/m  DLT: rash, thrombocytopenia
C16004 RRMM N = 52	PO, weekly (W), single agent	0.24-3.95 mg/m  , W MTD: 2.97 mg/m  DLT: rash, nausea, vomiting, diarrhea
C16005 NDMM N = 65	PO, W, combination with LenDex 28 day cycle	1.68-3.95 mg/m  , W MTD: 2.97 mg/m  DLT: nausea, vomiting, diarrhea, syncope RP2D*: 4.0 mg fixed (switched to fixed dosing in phase 2, relevant to 2.23 mg/m  )
C16006 NDMM N = 28	PO, TW (Arm A- 42 day cycle) and W (Arm B- 28 day cycle), combination with melphalan and prednisone	Arm A*: 3-3.7 mg, fixed dose, TW DLT: rash, thrombocytopenia, subileus Arm B*: 5.5 mg, fixed dose, W DLT: Esophageal ulcer
C16007 RR-AL N = 6	PO, W, single agent	4-5.5 mg, fixed dose*, W MTD: 4 mg DLT: thrombocytopenia, diarrhea, dyspnea, acute rise in creatinine, cardiac arrest
C16008 NDMM N=11	PO, TW, combination with LenDex 21 day cycle	3.0-3.7 mg fixed dose* W MTD: 4 mg DLT:
C16009 Solid tumors, Lymphomas N = 22	PO, W, single agent	5.5 mg fixed dose* W
C16010 RRMM N = 1	PO, W, combination with LenDex	4.0 mg fixed dose* W
TB- MC010034 RRMM N = 5	PO, W, single agent in 1 st part of study then in combination with LenDex in 2 nd part	3.0 mg fixed dose* W DLT: thrombocytopenia, nausea, hypertension, diarrhea

Abbreviations: RRAL = Relapsed or refractory Primary systemic light chain (AL) amyloidosis; BSA = body surface area ; DLT = dose-limiting toxicity; IV = intravenously; LenDex = lenalidomide plus dexamethasone; MTD = maximum tolerated dose; NDMM = newly diagnosed multiple myeloma; PO = orally; RRMM = relapsed and/or refractory multiple myeloma; RPh2D = recommended phase 2 dose

\* Approximate body surface area (BSA) and fixed dosing equivalence: 3 mg ~ equivalent to 1.68 mg/m^2 BSA dosing; 4.0 mg ~ equivalent to 2.23 mg/m^2 BSA dosing; and 5.5 mg ~ equivalent to 2.97 mg/m^2 BSA dosing.

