## **3. STUDY ENDPOINTS**

### **3.1 Primary Endpoints**

#### **Phase I:**

The primary endpoint is toxicity. Toxicity will be graded according to the NCI-Common Terminology Criteria for Adverse Events version 4.03. A DLT will be defined as any of the following toxicities that are at least possibly related to either Pomalidomide or MLN9708 and occur during cycle 1:

- Grade 4 neutropenia
- Grade 3 neutropenia with fevers  $\geq 38.5^{\circ}\text{C}$
- Grade 4 thrombocytopenia
- Grade 3 thrombocytopenia with bleeding

- Grade 3 or higher non-hematological toxicity will be considered dose limiting, with the following exceptions: diarrhea, fatigue, nausea or vomiting will only be considered dose limiting if, after 48 hours it has not recovered to <Grade 3 (despite maximal medical therapy), allergic reaction/hypersensitivity, or electrolyte/metabolic toxicity unable to be corrected to <Grade 1 or baseline within 48 hours will be considered dose limiting.
- Delay in starting cycle 2 on the scheduled day 1 for > 7 days due to treatment related toxicity
- Any dose modification or delay during cycle 1, except modifications/delays done in response to hypo- hyperthyroidism <=Grade 2, herpes zoster infection, all considered idiopathic or intrinsic to the underlying myeloma.

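### Cycle 1 serum chemistry is marked only on day 15 and the grid conflicts with footnote 5, so short-lived laboratory DLTs may be under-counted; running the panel on the weekly CBC draws is a cheap remedy

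*Combined protocol and SAP*

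**What the plan says.** In the Schedule of Events grid, the "Serum Chemistry" row is marked at screening, cycle 1 day 15, day 1 of later cycles and end of treatment. The cells for cycle 1 days 1, 8 and 22 are blank. The CBC row is marked on all four cycle 1 visits.

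Footnote 5 ties chemistry to the start of each cycle: "Serum Chemistry to be performed and reviewed by the investigator within 24 hours of day of dosing (first day of each cycle"). It also lists the panel: "Chemistry includes: glucose, calcium, albumin, total protein, sodium, potassium, BUN, creatinine, ALP, ALT, AST, bilirubin and uric acid".

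Sections 3.1 and 7.3 define a DLT over cycle 1: "Grade 3 or higher non-hematological toxicity will be considered dose limiting, with the following exceptions". One exception reads "electrolyte/metabolic toxicity unable to be corrected to <Grade 1 or baseline within 48 hours will be considered dose limiting". Creatinine, transaminases and bilirubin are not named among the exceptions and carry no minimum duration. Section 7.3 applies the same definition to unacceptable toxicity in phase II, and Section 10.1.5 uses that count to halt accrual at 2 of 6, 4 of 12 and 6 of 18 patients.

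**The concern.** The phase I primary endpoint is toxicity in cycle 1, and the MTD is the highest dose level with at most 1 DLT in 6 patients. A laboratory DLT can be scored only if a sample is taken while the value is abnormal. Neutropenia and thrombocytopenia are sampled weekly. Renal, hepatic and metabolic values are sampled every 14 days.

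The documents give reason to watch these values. Section 1.2.7 lists acute renal failure, increased creatinine and hyponatraemia among drug-related SAEs of MLN9708 with lenalidomide and dexamethasone, the closest combination described. Section 7.12 (Fluid Deficits) says acute renal failure has been reported with MLN9708. Renal toxicity is an adverse event of special interest. Section 1.5 calls the toxicity profile of the present combination unknown.

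Missed events push one way only: they make a dose look safer. With cohorts of six, one missed DLT separates 2/6 from 1/6. A phase I secondary objective, the time course and duration of adverse events and laboratory tests (Section 2.1.2), is also poorly served by 14-day sampling.

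**Working it through.** **Step 1. Read the grid.** Marks were read by column position. The MLN9708 row, which falls on days 1, 8 and 15 as the dosing schedule says, confirms the alignment.

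| Row | C1 D1 | C1 D8 | C1 D15 | C1 D22 | C2 D1 |
|---|---|---|---|---|---|
| MLN9708 (alignment check) | X | X | X | – | X |
| CBC | X | X | X | X | X |
| Serum chemistry, grid | – | – | X | – | X |
| Serum chemistry, footnote 5 | required | – | – | – | required |
| Toxicity Evaluation | X | – | – | – | X |

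Grid and footnote disagree on cycle 1 day 1. That sample is taken before or at first dosing, so it gives a baseline and cannot detect a DLT. The samples that can detect one are day 15 and cycle 2 day 1 (about day 29), 14 days apart.

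**Step 2. Chance that a scheduled sample falls inside an event.** Assumptions, none given in the documents: onset uniform over days 1 to 29, event lasting d days, no symptoms. With samples at days 15 and 29, the probability is 2d/28 = d/14, capped at 1. With samples at days 8, 15, 22 and 29, it is 4d/28 = d/7, capped at 1.

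| Duration d | Now (d/14) | Weekly (d/7) |
|---|---|---|
| 3 days | 21% | 43% |
| 5 days | 36% | 71% |
| 7 days | 50% | 100% |
| 14 days | 100% | 100% |

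These percentages count scheduled samples only, so they are a floor on true detection.

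**Step 3. Effect on the decision rule.** The plan's own figure first: Section 10.1.5 gives 0.64 for the chance of at least 2 of 6 patients at a true rate of 33%. The check is P(at most 1 of 6) = 0.67^6 + 6 × 0.33 × 0.67^5 = 0.0905 + 0.2673 = 0.358, and 1 − 0.358 = 0.642. It reproduces.

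Let s be the share of DLTs that are silent laboratory events and q the chance of catching one. The observed rate is 0.33 × (1 − s + s × q). The share s is also assumed; 10% to 50% shows the range. For 7-day events on the present schedule, q = 0.5:

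| s | Observed rate | P(at most 1 of 6) now | With full ascertainment |
|---|---|---|---|
| 10% | 0.3135 | 0.391 | 0.358 |
| 25% | 0.2888 | 0.445 | 0.358 |
| 50% | 0.2475 | 0.540 | 0.358 |

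Weekly samples catch every 7-day event (q = 1), so they give the last column. At s = 25%, the cumulative chance of a safety halt at 6, 12 and 18 patients falls from 0.642, 0.735 and 0.779 (the plan prints 0.64, 0.73 and 0.78) to 0.555, 0.637 and 0.676.

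Weekly sampling does not close the gap for very short events. For 3-day events at s = 25%, P(at most 1 of 6) is 0.498 now (q = 3/14) and 0.458 with weekly samples (q = 3/7).

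**The case against.** The case for leaving the schedule alone is substantial.

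- **Unscheduled tests are allowed.** The note under the grid provides for additional tests "at any reasonable time point during treatment if indicated for monitoring of drug profile/safety", and Section 7.7 has adverse events evaluated at each visit. So it would be wrong to infer that laboratory DLTs go unseen. These safeguards have limits: the note's asterisk sits on the Cycle 2+ and Day 15 headings, the grid marks Toxicity Evaluation in cycle 1 only on day 1, and visit review cannot reveal a silent value.
- **Persistent toxicity is caught.** Cycle 2 day 1 chemistry and the resolution criteria in Section 7.10 cover it. This stands; the gap concerns events that resolve between samples.
- **Not every abnormal value is an adverse event.** Section 11.3.2 requires that it be acted on or that the investigator judge it a clinically significant change. This stands and narrows the point, although nobody can judge a value that was not measured.
- **Reported frequencies favour a CBC-weighted schedule.** No chemistry abnormality reaches the thresholds for drug-related grade 3 or higher events in Table 1-4 or Table 1-6, and the SAE list in Section 1.2.7 gives no counts. This stands and argues for the lower end of the assumed range of s.

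Two further readings are tempting. Table 1-1 lists "DLT: thrombocytopenia, diarrhea, dyspnea, acute rise in creatinine, cardiac arrest" for Study C16007, which looks like a precedent. Section 1.2.6 shows that the creatinine rise was grade 2, at 5.5 mg, in an amyloidosis patient with renal involvement who also had dyspnea and cardiac arrest. It is not a silent grade 3 event at the doses tested here. A reader might also fault the calendar for holding no sample to serve the 48-hour rule. A recheck follows an abnormal result and cannot be a fixed visit, and electrolyte events corrected in time are not DLTs by definition.

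**Conclusion.** The point holds as a limited one. The grid and footnote 5 contradict each other on cycle 1 day 1. On either reading, scheduled chemistry able to detect a DLT is 14 days apart while CBC is weekly. A silent related grade 3 or higher laboratory toxicity that resolves between samples may be missed unless something prompts a test, and any such miss lowers the DLT and unacceptable-toxicity counts.

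The size cannot be derived from the documents. With uniform onset, scheduled detection of a 7-day event is 50% now and 100% weekly. With a true DLT rate of 33% and a 10% laboratory share, the chance of meeting the MTD criterion rises from 0.358 to 0.391. Larger shares give larger shifts, but nothing in the documents supports a particular share. A reader might infer that the RP2D will be biased. The documents do not show that: discretionary testing recovers some events, and Section 7.5 allows the RP2D to be set below the MTD. The case for change rests on low cost and a known direction of error.

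**What to change.** 1. Reconcile the Serum Chemistry row with footnote 5 for cycle 1 day 1, so that grid and footnote state the same requirement.
2. Run the chemistry panel on the CBC draws already scheduled on cycle 1 days 1, 8, 15 and 22, and mark the row accordingly.
3. As a secondary clarification in Sections 3.1 and 7.3, state how correction within 48 hours is documented: by a repeat value triggered by the abnormal result, not by a calendar sample. The electrolyte/metabolic criterion can then be scored the same way at every site.

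The cost is two extra panels per patient if day 1 chemistry is already drawn under footnote 5, and three if it is not. With at most 18 phase I patients plus 19 new phase II patients, that is at most 37 × 3 = 111 panels before replacements. No extra visit, blood draw or staff is needed. The protocol text appears twice in the combined document, so both copies should be changed.
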